9.4.2 Safety Endpoints

An initial description of safety measures is provided in Section 4.

Safety and tolerability will be assessed by clinical review of all relevant parameters including AEs and laboratory tests.

PDLC in Laboratory Parameters

For the summaries of laboratory tests, participants must have both a baseline and postrandomization on-treatment measurement to be included. Participants' laboratory values (based on their most abnormal laboratory test values, in the direction of interest, while on study intervention) will be classified as to whether or not they fall outside the PDLC and are worse in grade (ie, more abnormal in the direction of interest) than at baseline. The criteria will be adapted from the DAIDS Table for Grading the Severity of Adult and Pediatric Adverse Events, JUL-2017, version 2.1. A listing of the participants who meet the criteria will also be provided.

9.5 Analysis Populations

9.5.1 Efficacy Analysis Populations

The mITT will serve as the primary population for the analysis of efficacy data in this study. The mITT consists of all randomized participants who received at least 1 dose of study intervention. The primary objective will be assessed in the mITT-VN population, which consists of the subset of the participants in the mITT with undetectable SARS-CoV-2 in baseline NP swabs (ie, virus negative/undetectable at baseline). The mITT-VP population, consisting of the subset of the participants in the mITT with detectable SARS-CoV-2 in baseline NP swabs (ie, virus-positive/detectable at baseline) will be used in some of the exploratory analyses. Under certain extenuating circumstances (Section 8.2.5), eg, when only qualitative OP swab results are available from the central laboratory, qualitative OP swab results can be used to derive the baseline viral status.

A supportive analysis using the Per-Protocol population will be performed for the primary efficacy endpoint. The Per-Protocol population excludes participants from the mITT due to deviations from the protocol that may substantially affect the results of the primary efficacy endpoints. Participants with prophylaxis outcomes of "indeterminate" (Section 8.2.6) will be excluded from the Per-Protocol population. Moreover, participants who took <80% of the required doses will be excluded from the Per-Protocol population.

The final determination on protocol deviations, and thereby the composition of the Per-Protocol population, will be made prior to the final unblinding of the database and will be documented in a separate memo.

Due to the conflict in Ukraine, participants in Ukraine who were randomized in FEB-2022 with incomplete data for the primary endpoint (ie, no clinical outcome assessment on Day 14) will be excluded from the efficacy analyses in the mITT population.

9.5.2 Safety Analysis Populations

Safety Analyses will be conducted in the APaT population, which consists of all randomized participants who received at least 1 dose of study intervention. Participants will be included in the intervention group corresponding to the study intervention they actually received for the analysis of safety data using the APaT population. For most participants, this will be the

intervention group to which they are randomized. Participants who take incorrect study intervention for the entire treatment period will be included in the intervention group corresponding to the study intervention actually received.

At least 1 laboratory or vital sign measurement obtained subsequent to at least 1 dose of study intervention is required for inclusion in the analysis of the respective safety parameter. To assess change from baseline, a baseline measurement is also required.

9.6 Statistical Methods

This section describes the statistical methods that address the primary and secondary objectives. Methods related to exploratory objectives will be described in the sSAP. Methods related to analyses of biomarkers and other exploratory samples (Section 8.10) will be described separately.

Efficacy results that will be deemed to be statistically significant after consideration of the type I error control strategy are discussed in Section 9.8 and a description of the interim analysis is in 9.7. Statistical testing and inference for safety analyses are described in Section 9.6.2.

9.6.1 Statistical Methods for Efficacy Analyses

For the evaluation of the primary hypothesis, the superiority of MOV compared with placebo with respect to the percentage of participants with undetectable SARS-CoV-2 in baseline NP swabs developing COVID-19 by Day 14 will be assessed using the stratified Miettinen and Nurminen method with CMH weights [Miettinen, O. and Nurminen, M. 1985]. Stratification factors include age and household size as specified in Section 6.3.2. The primary hypothesis will be addressed by testing the null hypothesis $p_t \ge p_c$ versus the alternative hypothesis $p_t < p_c$, where p_t and p_c refer to event rates in MOV and placebo groups in participants with undetectable SARS-CoV-2 in baseline NP swabs, respectively. The null hypothesis will be rejected if the 1-sided p-value is less than 0.0249 (see Section 9.8 for alpha adjustment) and the superiority of MOV relative to placebo will be demonstrated for the primary endpoint.

For the analysis of this primary endpoint in the mITT-VN population, the following Table shows how to handle the indeterminate clinical outcomes of prophylaxis presented in Section 8.2.6 (Table 4).

Indeterminate Prophylaxis Outcomes	Imputation	
Lost to follow-up during or discontinued from the study prior to the window of interest (ie, prior to Visit 4 or Visit 6 for the outcome assessments conducted at those visits). This does not include participants who were already determined to be clinical failures prior to being lost to follow-up or discontinued.	Considered a case of COVID-19	
Death unrelated to COVID-19	Considered a case of COVID-19	
Missing the required viral test for confirmation of COVID-19 (see also Section 8.2.6 for details around acceptable windows)	Considered a case of COVID-19	
Other extenuating circumstances that preclude classification as a clinical success or failure (such as the participant receives another agent for the prevention of COVID-19)	Considered a case of COVID-19	
Participants in Ukraine who were randomized in FEB-2022 without clinical outcome assessment on Day 14 will be excluded from the efficacy analysis.		

Table 4 Imputation for Indeterminate Prophylaxis Outcomes

Moreover, a participant without a Day 14 clinical outcome assessment, but assessed as a clinical success through Day 29 will be treated as a clinical success through Day 14. A participant without a Day 29 clinical outcome assessment, but assessed as a clinical failure through Day 14 will be treated as a clinical failure through Day 29. If a participant discontinued from the study prior to the Day 14 or the Day 29 visit, but was assessed as a clinical failure from the COVID-19 Confirmation Visit, then the clinical failure should be carried forward to the Day 14 and/or the Day 29 visit after the COVID-19 Confirmation Visit. All other missing clinical outcome assessments will be imputed as clinical failures.

For the evaluation of the secondary hypothesis, the superiority of MOV compared with placebo with respect to the percentage of participants (regardless of SARS-CoV-2 results in baseline NP swabs) developing COVID-19 by Day 14 will be assessed using the same method in the primary hypothesis, ie, the stratified Miettinen and Nurminen method with CMH weights [Miettinen, O. and Nurminen, M. 1985] (stratified by age and household size as described in Section 6.3.2, and SARS-CoV-2 status in baseline NP swab). The secondary hypothesis will be evaluated by testing the null hypothesis $p_{ts} \ge p_{cs}$ versus the alternative hypothesis $p_{ts} < p_{cs}$, where p_{ts} and p_{cs} refer to event rates (percentages of participants developing COVID-19 by Day 14) in MOV and placebo groups, respectively. The null hypothesis will be rejected if the 1-sided p-value is less than 0.0249 (see Section 9.8 for alpha adjustment) and the superiority of MOV relative to placebo will be concluded for this secondary endpoint.

The efficacy of MOV compared with placebo for the prevention of COVID-19 with respect to the percentage of participants with undetectable SARS-CoV-2 in baseline NP swabs developing COVID-19 through Day 29 will be evaluated. The difference in percentages between treatment groups (MOV minus placebo) and the associated 95% CI will be

MK-4482-013-05 FINAL PROTOCOL

16-OCT-2022

calculated using the stratified Miettinen and Nurminen method with CMH weights [Miettinen, O. and Nurminen, M. 1985] (stratified by age and household size as described in Section 6.3.2).

For the evaluation of the prevention of viral transmission using MOV compared with placebo through Day 14 among participants with undetectable SARS-CoV-2 in NP swabs at baseline, the percentage of participants in the 2 intervention groups who have positive/detectable SARS-CoV-2 RNA through Day 14 will also be compared using the stratified Miettinen and Nurminen method [Miettinen, O. and Nurminen, M. 1985] (stratified by age and household size as described in Section 6.3.2).

The efficacy of MOV compared with placebo for the prevention of COVID-19 with respect to the percentage of participants with detectable SARS-CoV-2 in baseline NP swabs developing COVID-19 through Day 14 will be evaluated. The difference in percentages between treatment groups (MOV minus placebo) and the associated 95% CI will be calculated using the Miettinen and Nurminen method with CMH weights [Miettinen, O. and Nurminen, M. 1985].

A detailed analysis strategy for key efficacy endpoints is listed in Table 5.

Endpoint/Variable (Description, Time Point)	Primary vs Supportive Approach ^a	Statistical Method	Analysis Population	Missing Data Approach
Primary				
Percentage of participants with undetectable SARS-CoV-2 in baseline NP swabs developing COVID-19 by Day 14	Р	Stratified M&N method with CMH weights ^b	mITT-VN	As described in 9.6.1
Percentage of participants with undetectable SARS-CoV-2 in baseline NP swabs developing COVID-19 by Day 14	S	Stratified M&N method with CMH weights ^b	РР	Observed data only
Secondary				
Percentage of participants (regardless of SARS-CoV-2 results in baseline NP swabs) developing COVID-19 by Day 14	Р	Stratified M&N method with CMH weights ^b	mITT	As described in 9.6.1
Percentage of participants (regardless of SARS-CoV-2 results in baseline NP swabs) developing COVID-19 by Day 14	S	Stratified M&N method with CMH weights ^b	РР	Observed data only

Table 5	Analysis	Strategy	for Kev	Efficacy Endpoin	nts
1 4010 5	1 mary 515	Shategy	101 1109	Lineacy Linapon	110

Endpoint/Variable (Description, Time Point)	Primary vs Supportive Approach ^a	Statistical Method	Analysis Population	Missing Data Approach
Percentage of participants with undetectable SARS-CoV-2 in baseline NP swabs developing COVID-19 by Day 29	р	Stratified M&N method with CMH weights ^b	mITT-VN	As described in 9.6.1
Percentage of participants with undetectable SARS-CoV-2 in baseline NP swabs developing COVID-19 by Day 29	S	Stratified M&N method with CMH weights ^b	РР	Observed data only
Percentage of participants who develop positive/detectable SARS-CoV-2 through Day 14 among those with undetectable SARS-CoV-2 in NP swabs at baseline	р	Stratified M&N method with CMH weights ^b	mITT-VN	M=C ^c
Percentage of participants who develop positive/detectable SARS-CoV-2 through Day 14 among those with undetectable SARS-CoV-2 in NP swabs at baseline	S	Stratified M&N method with CMH weights ^b	РР	Observed data only
Percentage of participants with detectable SARS-CoV-2 in baseline NP swabs developing COVID-19 by Day 14	р	Stratified M&N method with CMH weights ^b	mITT-VN	As described in 9.6.1
Percentage of participants with detectable SARS-CoV-2 in baseline NP swabs developing COVID-19 by Day 14	S	Stratified M&N method with CMH weights ^b	РР	Observed data only

C=case of COVID-19; CMH=Cochran-Mantel-Haenszel; M=missing; M&N=Miettinen and Nurminen; mITT-VN=modified intent-to-treat population with undetectable SARS-CoV-2 in baseline NP swabs; NP=nasopharyngeal; PP=per-protocol.

^a P=Primary approach; S=Supportive approach.

^b Miettinen and Nurminen method with CMH weights stratified by age and household size.

^c M=C is Missing considered as a case of COVID-19.

Participants in Ukraine who were randomized in FEB 2022 without clinical outcome assessment on Day 14 will be excluded from the efficacy analysis.

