4.2.1 Rationale for Endpoints

4.2.1.1 Efficacy Endpoints

The primary efficacy endpoint for the study, COVID-19 (laboratory-confirmed SARS-CoV-2 infection with symptoms), was selected in accordance with the US FDA guidance on development of drug and biological products for treatment or prevention of COVID-19 [Food and Drug Administration 2021]. Development of symptomatic disease represents a clinically meaningful endpoint for participants since it demonstrates the onset of deleterious effects they can directly perceive. A COVID-19 case for the study is defined as a participant with qualifying symptoms of COVID-19 with onset through Day 14 (for the primary endpoint) and SARS-CoV-2 detected by central laboratory RT-PCR testing from a sample collected at the COVID-19 Confirmation Visit. Laboratory-confirmed COVID-19 with onset through Day 29 will also be assessed as an exploratory endpoint. The onset of COVID-19 is determined by the day of onset of symptoms, rather than the day of the COVID-19 Confirmation Visit. Therefore, the day of onset of COVID-19 symptoms supports the primary endpoint, even if the day of the COVID-19 Confirmation Visit is later than Day 14. The qualifying symptoms of COVID-19 are provided in Section 8.2.2.

The study will evaluate SARS-CoV-2 RNA as a secondary endpoint through Day 14 (and as an exploratory endpoint through Day 29) to assess the impact of MOV on preventing viral transmission in participants with undetectable SARS-CoV-2 in baseline NP swabs. Viral transmission, even in the absence of symptoms, represents an important outcome with regards to infection control. This is best evaluated via RT-PCR detection of SARS-CoV-2 RNA since nucleic acid amplification offers the most sensitive method for assessment of viral transmission. For this reason, SARS-CoV-2 RNA has been selected as the appropriate endpoint.

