8.2.6 Assessment of Prophylaxis Outcome

The clinical outcome of prophylaxis will be assessed at the Day 14 and Day 29 visits for all participants and at the COVID-19 Confirmation Visit for participants who develop laboratory-confirmed COVID-19 with symptoms (see Section 1.3.1). Assessments should be made according to the following definitions:

Term	Definition		
Clinical Success	The participant does not develop laboratory-confirmed COVID-19 with onset within the window of interest (ie, symptom onset on or before Day 14 for the Visit 4 assessment; and on or before Day 29 for Visit 6 assessment).		
	Note: Participants who remain asymptomatic through Day 14 (or Day 29, for the Day 29 endpoint) are also considered clinical successes regardless of SARS-CoV-2 results (positive, negative, or missing).		
Clinical Failure	The participant develops laboratory-confirmed COVID-19 with onset within the window of interest (ie, symptom onset on or before Day 14 for the Visit 4 assessment; and on or before Day 29 for Visit 6 assessment).		
	The date of onset is considered the date of onset of symptoms. Note: An assessment of "Clinical Failure" on or before Day 14/Visit 4 will also be carried forward to the Day 29/Visit 6 assessment.		
Indeterminate	The outcome is indeterminate if any of the following apply:		
	• The participant is lost to follow-up during or has discontinued from the study prior to the window of interest (ie, prior to Visit 4 or Visit 6 for the outcome assessments conducted at those visits).		
	Note: This definition does not apply to participants who developed laboratory-confirmed COVID-19 with symptoms prior to leaving the study. For those participants, prophylaxis outcome should be assessed as "Clinical Failure" per the definition above.		
	• Death unrelated to COVID-19.		
	• The participant is symptomatic and missing the required viral test for confirmation of COVID-19.		
	Note: A virus-detectable NP swab collected within +/-5 days of symptom onset is considered to be within an acceptable window to confirm onset of COVID-19. A virus-undetectable NP swab that is collected within 5 days after symptom onset is considered to be within an acceptable window to rule out COVID-19.		
	NP swabs collected outside these windows are considered missing.		
	• There are other extenuating circumstances that preclude classification as a clinical success or failure, such as:		

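### The Day 14 endpoint is defined by date of symptom onset, but its imputation rules are tied to the Visit 4 assessment, so a few participants documented as case-free through Day 14 can be counted as cases

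*Combined protocol and SAP*

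**What the plan says.** **Endpoint.** Section 4.2.1.1 fixes the time of the event by symptom onset: "the day of onset of COVID-19 symptoms supports the primary endpoint, even if the day of the COVID-19 Confirmation Visit" comes after Day 14. Section 8.2.6 defines success and failure at Visit 4 in the same way, by onset on or before Day 14. A note there adds that participants who stay asymptomatic through Day 14 "are also considered clinical successes regardless of SARS-CoV-2 results (positive, negative, or missing").

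**Indeterminate outcomes.** Section 8.2.6 makes the outcome indeterminate when the participant is lost to follow-up or "has discontinued from the study prior to the window of interest (ie, prior to Visit 4 or Visit 6"). Table 4 counts that as a case of COVID-19. The only exception in that row is for known failures: "This does not include participants who were already determined to be clinical failures prior to being lost to follow-up or discontinued".

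**Missing assessments.** Section 9.6.1 lets a participant with no Day 14 assessment "but assessed as a clinical success through Day 29 will be treated as a clinical success through Day 14". Failures are carried forward from Day 14 or from a Confirmation Visit. Then "All other missing clinical outcome assessments will be imputed as clinical failures".

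**Timing and data.** The Schedule of Activities (1.3.1) allows Visit 4 from Day 14 to Day 17. It schedules the prophylaxis outcome assessment at Day 14, Day 29 and Confirmation Visits, but not at Day 21. The symptom diary is daily through Day 29 (8.2.1). Section 8.11.3 asks participants who withdraw after the end-of-treatment visit and before the Day 14 visit to complete the Day 14 activities when they withdraw.

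**The concern.** The endpoint asks whether symptoms began by Day 14. The imputation asks whether an assessment was made at a visit that can fall three days later. Evidence from Days 15 to 28 that a participant was case-free at Day 14 can enter the Day 14 outcome only through a completed Day 29 success.

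Where the two questions give different answers, the primary analysis can count as a case someone whose own dated record says otherwise. In one situation the Day 14 outcome is settled by events after Day 14: a missed Visit 4 becomes a success if the participant stays well to Day 29 and a failure if illness begins on Day 22. In another, two rules apply to the same person and two programmers could derive different primary outcomes. At stake are a diluted relative effect, some power, and a possible bias if the affected participants are unevenly split between arms.

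**Working it through.** **Step 1: trace each type of participant through the rules.**

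| Participant | By onset date (4.2.1.1, 8.2.6) | By Table 4 and 9.6.1 |
|---|---|---|
| Misses Visit 4, well, assessed as success at Day 29 | Non-case | Non-case (carried back) |
| A. Misses Visit 4, first confirmed onset on Days 15 to 29 | Non-case | Case: not a Day 29 success, so the catch-all applies |
| B. Misses Visit 4, diary or later contact documents no qualifying symptoms through Day 14, leaves before Day 29 | Non-case | Case: no Day 29 assessment, so the catch-all applies |
| C. Asymptomatic through Day 14, leaves before a Visit 4 due by Day 17 | Success, by the 8.2.6 note | Case, by the rule on leaving before Visit 4; precedence not stated |
| Leaves before Day 14 | Unknown | Case (not in dispute) |

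**Step 2: reproduce the planned power.** Inputs from 9.9.1 and Table 7: 550 per arm, placebo 8%, MOV 3.2%. Final one-sided alpha is 0.0249 (9.6.1).

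- Standard error = sqrt(0.08 × 0.92/550 + 0.032 × 0.968/550) = 0.01379.
- Power = Φ(0.048/0.01379 − 1.962) = 93.6%, or 93.3% after the loss from the futility look. Table 7 states 93%.
- The same unpooled formula gives 89.4, 90.6, 93.6, 94.1 and 94.5% for the five rows of Table 7, against the stated 89, 90, 93, 94 and 94%.

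**Step 3: effect of imputing true non-cases.** Let f be the share of true non-cases imputed as cases. Each rate becomes p + f(1 − p), so with equal f the risk difference is multiplied by (1 − f). The documents give no value for f; the range is an assumption.

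| f, both arms | Placebo | MOV | Difference (points) | Relative reduction | False cases in 1100 | Power |
|---|---|---|---|---|---|---|
| 0 | 8.00% | 3.20% | -4.80 | 60% | 0 | 93.6% |
| 0.5% | 8.46% | 3.68% | -4.78 | 56.5% | 5 | 91.5% |
| 1% | 8.92% | 4.17% | -4.75 | 53% | 10 | 89.2% |
| 2% | 9.84% | 5.14% | -4.70 | 48% | 21 | 84.5% |

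Example at 2%: placebo 0.08 + 0.02 × 0.92 = 0.0984; MOV 0.032 + 0.02 × 0.968 = 0.0514; relative reduction 1 − 0.0514/0.0984 = 48%.

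**Step 4: unequal f (assumed; pooled-variance formula, 550 per arm, baseline power 93.4%).**

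- 2% in MOV and 1% in placebo: difference 5.14% − 8.92% = -3.78 points, power 69%.
- 1% in MOV and 2% in placebo: difference 4.17% − 9.84% = -5.67 points, power 96%.
- No true effect (8% in both arms), with 1% in MOV and 2% in placebo: apparent rates 8.92% and 9.84%, and one-sided rejection in about 7.5% of trials instead of 2.49%.

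**Step 5: scale of type A alone.** With an assumed 5% missing Visit 4 and an assumed 3% having onset on Days 15 to 29, 550 × 0.05 × 0.03 = 0.8 participants per arm.

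**The case against.** A reader might infer that attendance at Visit 4 decides the primary outcome, and that anyone who skips it becomes a false case. The documents do not support that. The definition rests on onset date, and a missed Visit 4 followed by a Day 29 success is already a Day 14 success.

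A reader might also take type C as a settled misclassification. It is not. The note in 8.2.6 makes that participant a success, and 8.11.3 asks for the Day 14 activities, which include the outcome assessment, at withdrawal. What remains is that Table 4 neither says which rule prevails nor whether an assessment made at withdrawal counts.

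Type B can be overstated too. The diary is on paper and its pages are collected at clinic visits, while Day 21 is designated a virtual visit with no outcome assessment. Someone who skips Visit 4 and then leaves may never return the relevant pages. Without pages or a documented contact covering Day 14, treating the outcome as missing is defensible.

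It is tempting to say that the rule penalises an arm in which onset is delayed. Type A does work in that direction, but on the illustrative rates above it involves less than one participant per arm.

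Finally, counting missing as failure is prespecified for both arms, the tested quantity is the risk difference, and equal misclassification hardly moves it. All of that stands. However, the supportive per-protocol analysis does not cure the problem: it excludes indeterminate outcomes and uses observed data only (9.5.1, Table 5), so it does not restore these participants as non-cases. Section 9.6.1 and Table 5 offer no other sensitivity analysis of this imputation.

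**Conclusion.** The point holds in a limited form. For types A and B the written rules give a result that the trial's own dated records can contradict; for B, only where diary pages or a later contact actually document Day 14 status. For type C the text contradicts itself and must be reconciled.

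Probably few participants are affected. On the assumed 0.5% to 2% of true non-cases, equal in both arms, the risk difference loses at most 0.1 point. The larger costs are in the relative reduction (60% to between 56.5% and 48%) and in power (about 93% to between 91.5% and 84.5%). These are ranges under assumption, not estimates. Unequal shares could bias the difference in either direction, but nothing in the documents indicates an imbalance.

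**What to change.** In 9.6.1 and Table 4, with 8.2.6 aligned, derive the Day 14 outcome in this order:

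1. Failure if confirmed onset is on or before Day 14.
2. Otherwise, impute a case if a qualifying symptomatic episode with onset by Day 14 lacks an in-window swab, or if another Table 4 indeterminate reason arises by Day 14 (death unrelated to COVID-19, another preventive agent, other extenuating circumstance).
3. Otherwise, success if collected diary pages or a later documented contact cover Day 14 with no unresolved qualifying symptoms. This includes participants whose first confirmed onset is after Day 14.
4. Otherwise, where symptom status through Day 14 is not documented, keep the imputation as a case.

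The order matters. Someone with unswabbed qualifying symptoms on Day 10 and confirmed onset on Day 22 would otherwise fit both rule 2 and rule 3; rule 2 takes precedence.

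In 8.2.6 and Table 4, replace the condition of leaving before Visit 4 or Visit 6 with leaving before symptom status through Day 14 or Day 29 is documented. State that an outcome assessment made at a withdrawal visit on or after Day 14 counts.

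The cost is wording and programming. Section 9 requires a protocol amendment for changes to the methods for the primary hypothesis, made before unblinding. No new procedure is needed: the daily diary, onset dates and the Day 21 and Day 29 contacts are already in the schedule, although rule 3 can use only diary pages that were actually returned.

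### The Ukraine exclusion looks only at Day 14, so a Day 14 success whose Day 29 assessment was lost to the conflict is counted as a COVID-19 case in the Day 29 secondary endpoint

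*Combined protocol and SAP*

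**What the plan says.** The exclusion is stated three times, each time with a Day 14 trigger.

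- Section 9.5.1 removes from the mITT efficacy analyses "participants in Ukraine who were randomized in FEB-2022 with incomplete data for the primary endpoint (ie, no clinical outcome assessment on Day 14").
- The note to Table 4 in Section 9.6.1 reads: "Participants in Ukraine who were randomized in FEB-2022 without clinical outcome assessment on Day 14 will be excluded from the efficacy analysis".
- The footnote to Table 5, which also covers the Day 29 rows, repeats this: "Participants in Ukraine who were randomized in FEB 2022 without clinical outcome assessment on Day 14 will be excluded from the efficacy analysis".

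Table 5 lists the Day 29 secondary endpoint, "Percentage of participants with undetectable SARS-CoV-2 in baseline NP swabs developing COVID-19 by Day 29". Its primary approach uses mITT-VN and takes its missing-data handling from Section 9.6.1. That section contains three relevant rules.

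- Table 4 scores loss to follow-up or discontinuation as a case of COVID-19 when it happens "prior to Visit 4 or Visit 6 for the outcome assessments conducted at those visits". Visit 6 is the Day 29 visit.
- Only failures pass from Day 14 to Day 29: "A participant without a Day 29 clinical outcome assessment, but assessed as a clinical failure through Day 14 will be treated as a clinical failure".
- Everything left over is a failure: "All other missing clinical outcome assessments will be imputed as clinical failures".

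**The concern.** By writing the exclusion, the sponsor has accepted that an assessment lost to the conflict is not evidence of disease. That judgement is applied at Day 14 but not at Day 29. A participant who completed Day 14 as a success and then lost Day 29 to the same cause stays in mITT-VN and is scored as a case.

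What is at stake is the primary-approach result for the Day 29 secondary endpoint: both event rates, the risk difference and its CI. Cases unrelated to drug or virus would be added to each arm. The Day 14 and Day 29 results could then look inconsistent for a reason that has nothing to do with how long protection lasts.

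**Working it through.** **Tracing one participant.** Take a participant in Ukraine in mITT-VN with a Day 14 success and no Day 29 assessment.

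1. Exclusion (Section 9.5.1, notes to Tables 4 and 5): not met, because the Day 14 assessment exists.
2. Carry-forward to Day 29 (Section 9.6.1): not met, because only failures are carried.
3. Table 4 (loss before Visit 6) or the residual rule: met, so the participant is a Day 29 case.

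**Is the timing possible?** With Day 1 as randomization, Day 14 falls 13 days later and Day 29 falls 28 days later. For randomization from 1 to 28 February 2022, Day 14 falls from 14 February to 13 March and Day 29 from 1 to 28 March. Assume steady enrolment and a single date S on which visits stop. Randomization in the 13 days up to S loses Day 14. Randomization in the 15 days before that (28 - 13) keeps Day 14 but loses Day 29. The second group need not be smaller than the first. If S falls before 1 March, part of the second group was randomized in January.

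**Inputs.** The planning rates are 8% placebo and 3.2% MOV, with 550 per arm and final one-sided alpha 0.0249 (Sections 9.6.1 and 9.9.1). These rates are for Day 14 and stand in for Day 29. The number affected, k, is an assumption.

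**Reproducing the plan's figure first.** SE = sqrt[(0.08 x 0.92 + 0.032 x 0.968)/550] = 0.01379. Power = Phi(0.048/0.01379 - 1.962) = 93.6%, against 93% in Table 7. The same formula gives 89.4, 90.6, 94.1 and 94.5% for the unequal rows, against 89, 90, 94 and 94%. The inputs are therefore read correctly.

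**Current rule, even split.** With m = k/2 affected per arm, the arm rate is [(550 - m)p + m]/550. The Wald half-width, 1.96 x SE, stands in for the planned stratified Miettinen and Nurminen interval.

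| k | MOV cases (rate) | Placebo cases (rate) | Difference, points | CI half-width | Relative reduction |
|---|---|---|---|---|---|
| 0 | 17.6 (3.20%) | 44.0 (8.00%) | -4.80 | 2.70 | 60% |
| 10 | 22.4 (4.08%) | 48.6 (8.84%) | -4.76 | 2.89 | 54% |
| 20 | 27.3 (4.96%) | 53.2 (9.67%) | -4.71 | 3.07 | 49% |
| 40 | 37.0 (6.72%) | 62.4 (11.35%) | -4.63 | 3.38 | 41% |

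**Uneven split, k = 20.**

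- 15 MOV and 5 placebo: (535 x 0.032 + 15)/550 = 5.84% and (545 x 0.08 + 5)/550 = 8.84%. The difference is -3.00 (CI -6.07 to 0.08).
- 5 MOV and 15 placebo: the difference is -6.43 (CI -9.48 to -3.38).
- Under independent 1:1 allocation, the chance of 15 or more of 20 in MOV is 21,700/1,048,576 = 2.1%.

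**Two ways to exclude, k = 20, 10 affected per arm.**

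- Regardless of Day 14 outcome: 540 per arm, difference -4.80 (CI -7.53 to -2.07).
- Day 14 successes only: MOV 17.6/(550 - 9.68) = 3.26%, placebo 44/(550 - 9.2) = 8.14%, difference -4.88. At k = 40 it is 17.6/530.64 - 44/531.6 = -4.96. MOV has more successes, so its denominator shrinks more and the result tilts in its favour. The size, 0.08 and 0.16 points, is about that of the shift toward the null under the current rule (0.09 and 0.17).

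**The case against.** The strongest reply has five parts.

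1. *Nothing confirmatory depends on it.* This stands. H1 and H2 are both Day 14 hypotheses (Section 9.8), and Day 29 is reported as a difference with a 95% CI. A reader might infer that power or the trial's conclusion is at risk. The plan performs no alpha-controlled Day 29 test, so there is no such power to lose.
2. *The planned estimate hardly moves.* This stands for an even split: at most 0.17 points at k = 40. The relative reduction falls much more, but Section 9.6.1 specifies the difference in percentages. The wider CI and the sensitivity to an uneven split remain.
3. *An unimputed analysis already exists.* This stands in part. Table 5 has a Per-Protocol row for Day 29 on observed data. It is supportive only, and that population also drops participants who took under 80% of doses.
4. *A missed clinic visit is not always a missing outcome.* This stands as a limit on the count. Home or alternate-site visits are allowed, symptoms are recorded daily through Day 29, and Section 8.2.6 counts participants who stay asymptomatic through Day 29 as successes even without swabs. It does not help where no Day 29 assessment was made: Section 8.2.6 makes the outcome indeterminate when "The participant is lost to follow-up during or has discontinued from the study prior to the window of interest".
5. *Table 4 is introduced for the primary endpoint.* This does not stand. Table 4 names Visit 6, Table 5 sends the Day 29 row to Section 9.6.1, and the residual rule applies in any case.

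Missing-equals-failure can be defended as deliberately conservative. The sponsor has already set it aside for this cause at Day 14, and no reason is given for keeping it at Day 29.

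**Conclusion.** The point holds as a narrow inconsistency in the primary approach to one secondary endpoint. The same cause of missingness leads to exclusion at Day 14 and is scored as disease at Day 29.

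Its size is unknown. The documents give no Ukrainian enrolment, no date when visits stopped and no count of lost Day 29 assessments, and the number affected could be near zero. The figures above rest on assumed counts, Day 14 rates used for Day 29, equal arms and a Wald interval. On those terms the effect is a small shift toward the null, a wider CI and inflated event rates in both arms, with a larger shift in either direction if the affected participants happen to split unevenly.

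A reader might also infer that the exploratory Day 29 COVID-19 endpoints are affected. The documents do not support that: Section 9.6 leaves exploratory methods to the supplemental SAP, and Table 5 covers only primary and secondary endpoints.

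**What to change.** Make the exclusion endpoint-specific in Sections 9.5.1 and 9.6.1 and in the notes to Tables 4 and 5. For the Day 29 secondary endpoint:

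- Exclude participants in Ukraine whose Day 29 visit fell due after site visits stopped.
- Identify them before unblinding, on a blinded list built from country and due date, with the stopping date documented.
- Do not limit the rule to February 2022 randomization.
- Apply it regardless of Day 14 outcome, so that failures are not kept while successes are dropped.
- Report the number excluded by arm.
- Show the result under the present missing-equals-failure rule as a sensitivity analysis.

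The cost is a short text change, one blinded listing and one extra analysis. Section 9 allows changes to non-confirmatory analyses to be recorded in the supplemental SAP before unblinding. The downside is slightly fewer participants in the Day 29 analysis, with some observed Day 14 outcomes set aside there. Made after unblinding, the same change would look post hoc.
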